7.2. Study Flowcharts

Figure 5 shows the dosing schedule for each 42-day cycle in the Part A and Part C monotherapy portions of the trial, while Figure 6 shows Part B combination therapy portions of the trial. Inpatient stays are only required in Cycle 1.

Figure 5: Part A and Part C: XmAb18087 Monotherapy Treatment

[figure not shown]
[figure not shown]

Figure 6: Part B: XmAb18087/Pembrolizumab Combination Therapy Treatment

7.3. Dosing Schedule

Each subject will be administered XmAb18087 IV at a constant infusion rate over

Version 1.0 Page 44 of 145

The initial treatment period for each subject in this study is 1 cycle. Each cycle is 42 days long. In Part A and Part C, each cycle will consist of 6 weekly doses of XmAb18087 (on Days 1, 8, 15, 22, 29, and 36).

In Part B, each cycle will consist of 5 XmAb18087 doses on Days 1, 8, 22, 29, and 36. Pembrolizumab will be administered as 1 dose during each 42-day cycle, on Day 15.

Part A dose levels are defined in Table 2. Part B dose levels are defined in Table 3. Part C dose levels are defined in Table 4.

The dose is based on the subject's actual baseline weight measurement in kilograms (rounded to the nearest integer) on Day -1. Following the first dose at any dose level, the weight used for calculation of subsequent doses will be modified only if the subject's weight changes by more than 10% from the baseline weight, at which point the dose will be recalculated using the current weight (rounded to the nearest integer).

Version 1.0 Page 45 of 145

Table 2: Part A (MCC) Monotherapy Safety Run-in and Expansion Cohorts

					Cycle	e 1						Cycle	2+			Subjects
	Cycle and Day	D1	D8	D15	D22	D29	D36	D40	D1	D8	D15	D22	D29	D36	D40	
	•							± 2							± 2	
	Drug			XmA	b1808	7		EA			XmAb	18087			EA	
				(με	g/kg)						(μg/	kg)				
	1	8	15	22	29	36	40	43	50	57	64	71	78	82		
Part A	1A	0.3	1.0	1.0	1.0	1.0	1.0		1.0	1.0	1.0	1.0	1.0	1.0		3 - 6
(Safety	2A	0.3	1.0	2.0	2.0	2.0	2.0		2.0	2.0	2.0	2.0	2.0	2.0		3 - 6
Run-in)	3A	0.3	1.0	2.0	4.0	4.0	4.0		4.0	4.0	4.0	4.0	4.0	4.0		3 - 6
Part A (Expansion)	Expansion A							At	RD coho	rt						Up to 22

D = day; EA = efficacy assessment (no drug administered); MCC = Merkel cell carcinoma; RD = recommended dose. Maximum escalated dose for each cohort in bold.

Version 1.0 Page 46 of 145

Table 3: Part B (MCC) Combination Therapy Safety Run-in and Expansion Cohorts

	Cycle			(Cycle 1						(Cycle 2	+			Subjects
	and Day	D1	D8	D15	D22	D29	D36	D40	D1	D8	D15	D22	D29	D36	D40	
								± 2							± 2	
	Drug	XmAb (μg/		Pem (mg)	X	mAb18 (μg/kg		EA	XmAb (μg/		Pem (mg)	X	mAb18 (μg/kg		EA	
	Study Day	1	8	15	22	29	36	40	43	50	57	64	71	78	82	
	1B	0.3	0.3	400	0.3	0.3	0.3		0.3	0.3	400	0.3	0.3	0.3		3 - 6
Part B	2B	0.3	1.0	400	1.0	1.0	1.0		1.0	1.0	400	1.0	1.0	1.0		3 - 6
(Safety Run-in)	3B	0.3	1.0	400	1.0	2.0	2.0		2.0	2.0	400	2.0	2.0	2.0		3 - 6
	4B	0.3	1.0	400	1.0	2.0	2.0		2.0	4.0	400	4.0	4.0	4.0		3 - 6
Part B (Expansion)	Expansion B							At RE	ochort cohort							Up to 30

18 August 2020

D = day; EA = efficacy assessment (no drug administered); MCC = Merkel cell carcinoma; Pem = pembrolizumab; RD = recommended dose. Maximum escalated dose for each cohort in bold.

Version 1.0 Page 47 of 145

Table 4: Part C (SCLC) Monotherapy Safety Run-in and Expansion Cohorts

					Cycle	e 1						Cycle	2+			Subjects
	Cycle and Day	D1	D8	D15	D22	D29	D36	D40	D1	D8	D15	D22	D29	D36	D40	
								± 2							± 2	
	Drug			XmA	b1808	7		EA			XmAb	18087			EA	
	(μg/kg) (μg/kg)															
	Study Day	1	8	15	22	29	36	40	43	50	57	64	71	78	82	
Part C	1C	0.3	1.0	1.0	1.0	1.0	1.0		1.0	1.0	1.0	1.0	1.0	1.0		3 - 6
(Safety	2C	0.3	1.0	2.0	2.0	2.0	2.0		2.0	2.0	2.0	2.0	2.0	2.0		3 - 6
Run-in)	3C	0.3	1.0	2.0	4.0	4.0	4.0		4.0	4.0	4.0	4.0	4.0	4.0		3 - 6
Part C (Expansion)	Expansion C							At l	RD coho	rt						Up to 30

18 August 2020

Version 1.0 Page 48 of 145

D = day; EA = efficacy assessment (no drug administered); RD = recommended dose; SCLC = small cell lung cancer. Maximum escalated dose for each cohort in bold.

7.4. Continuation/Discontinuation of Therapy

There will be a pretreatment tumor assessment, followed by a reassessment after each treatment cycle (Table 7).

7.4.1. Continuation Prior to Progression

Subjects who appear to benefit from XmAb18087 or XmAb18087/pembrolizumab combination therapy may continue to receive additional drug treatment until unacceptable toxicity develops, progression occurs, or the Investigator thinks there is no longer clinical benefit to the subject.

To receive study drug past the first cycle, a subject in Part A or Part C must also satisfy the following criteria:

- Does not meet any criteria for stopping dosing (Section 7.8 and Section 10.3)
- Has recovered from any toxicity to \leq Grade 2 or to baseline
- Has experienced clinical benefit, as assessed by the Investigator

To receive combination therapy past the first cycle, a subject in Part B must satisfy all continuation criteria for Part A and Part C, and, in addition, must have recovered sufficiently from any immune-related adverse event so that he/she is eligible for continuation/re-initiation of study treatment. Refer to Section 7.4 and the pembrolizumab label (Keytruda® Package Insert, 2020) for dose modification and toxicity management guidelines.

For subjects who continue to receive XmAb18087 or XmAb18087 and pembrolizumab combination therapy past the first cycle, tumor assessments will be repeated after every cycle of therapy.

7.4.3. Intrasubject Dose Escalation

Intrasubject dose escalation of XmAb18087 is permitted in the study. The subject must meet the following criteria in order to be eligible for treatment at the higher dose level:

- The subject tolerates his/her dose level of XmAb18087
- The subject meets criteria for continuation of therapy prior to progression (Section 7.4.1)
- All subjects in the safety run-in cohort at the next higher dose level have completed the
 first cycle of treatment, and the SRC has made the decision that the higher dose level
 is tolerable

No dose escalation will be permitted for pembrolizumab.

For MCC subjects, crossover from monotherapy (Part A) to combination therapy (Part B) is not permitted. Subjects in Part B may not escalate more than once.

7.5. Number of Subjects

Up to 142 subjects will be enrolled; the total number required will depend on the number of safety run-in cohorts required to define each RD for expansion in Part A, Part B, and Part C. Up to 25 clinical investigation sites in the US will enroll subjects in this study.

7.6. Treatment Assignment

Subject Screening Number: Subjects who consent for the study will be assigned a Subject Screening Number.

Subject Enrollment Number: Subjects eligible to receive study treatment will be assigned a Subject Enrollment Number.

Enrolled subjects will be assigned to a cohort as follows:

- Subjects with advanced MCC who have received prior treatment with or are ineligible for treatment with anti-PD1 and/or anti-PDL1 will be assigned to a monotherapy cohort in Part A
- Subjects with advanced MCC who are anti-PD1 and anti-PDL1 therapy naïve and who do
 not have a contraindication to anti-PD1 therapy will be assigned to a combination therapy
 cohort in Part B.

Version 1.0 Page 50 of 145

• Subjects with extensive stage SCLC who have received prior treatment with standard therapies will be assigned to a monotherapy cohort in Part C.

7.7. Safety Run-in Cohorts

In each safety run-in cohort, no more than 1 subject will be initiated on treatment with XmAb18087 on any given day.

The planned initial XmAb18087 dose for all cohorts is $0.3 \,\mu\text{g/kg}$. Subsequent doses will then be escalated in steps (except for Cohort 1B, which will use $0.3 \,\mu\text{g/kg}$ for all doses) as indicated in Table 2, Table 3, and Table 4 in an effort to reduce the incidence and severity of CRS.

For all safety run-in cohorts in Part A, Part B, and Part C, the SRC will decide whether to advance to the next higher dose level cohort based on review of all available safety data. For each cohort, 3 subjects will be initially enrolled. If no subject experiences an adverse event of specific concern (AESC, as defined in Section 7.8 below), the SRC will be convened after all 3 subjects have completed one treatment cycle or discontinued treatment, whichever comes first. If 1 of the initial 3 subjects experiences an AESC, 3 additional subjects will be enrolled in that cohort (up to a total of 6 subjects) prior to convening the SRC. If 2 subjects experience an AESC, no additional subjects will be enrolled until the SRC has convened and made a recommendation based on the available safety data. Based on the type and severity of toxicities observed, the SRC may modify the safety run-in scheme (eg, decreases in dose level, smaller escalation steps, or other changes in the regimen), as long as the changes do not significantly affect the risk profile of the study.

If a subject discontinues treatment prior to completion of the first cycle due to an AE, that subject will not be replaced. If a subject discontinues treatment prior to completion of the first cycle for any other reason, an additional subject may be enrolled as a replacement.

Part A will begin by enrolling 3 to 6 subjects in Cohort 1A. After Cohort 1A dosing is demonstrated to be tolerable and is approved by the SRC, Part B will begin by enrolling Cohort 1B, which is one dose level lower than Cohort 1A.

Part C may begin concurrently with Part A.

The safety run-in portion will continue until establishment of an RD for expansion or until the repeated dose level reaches the highest dose planned in this study.

Enrolling additional subjects beyond 142 will require a protocol amendment.

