Part B, which will enroll subjects with advanced MCC not previously treated with anti-PD1 or anti-PDL1 agents, consists of safety run-in cohorts followed by an expansion cohort. Safety run-in Cohort 1B (one dose level below Cohort 1A) will begin enrolling after Cohort 1A is completed and the dosing regimen is deemed tolerable. For all Part B cohorts, 400 mg pembrolizumab will be administered IV on Day 15 of each 42-day cycle. Three to 6 subjects will be enrolled in Cohort 1B and will receive XmAb18087 administered IV as follows: 0.3 μ g/kg on Days 1, 8, 22, 29, and 36 of all cycles. If this regimen is tolerated, 3 to 6 additional safety run-in subjects will be enrolled in Cohort 2B and will receive step-up IV dosing of XmAb18087 as follows: 0.3 μ g/kg on Day 1, then 1.0 μ g/kg on Days 8, 22, 29, and 36 of the first cycle and Days 1, 8, 22, 29, and 36 of all subsequent cycles. If this regimen is tolerated, 3 to 6 subjects will be enrolled in Cohort 3B and will receive step-up IV dosing of XmAb18087 as follows: 0.3 μ g/kg on Day 1, 1.0 μ g/kg on Days 8 and 22, then 2.0 μ g/kg on Days 29 and 36 of the first cycle and Days 1, 8, 22, 29, and 36 of all subsequent cycles. If this regimen is tolerated, 3 to 6 subjects will be enrolled in Cohort 4B and will receive step-up IV dosing of XmAb18087 as follows: 0.3 μ g/kg on Day 1, 1.0 μ g/kg on Days 8 and 22, 2.0 μ g/kg on Days 29 and 36 of the first cycle and Day 1 of all subsequent cycles, and 4.0 μ g/kg and Days 1, 8, 22, 29, and 36 of all cycles after the first cycle. See Cohort Table B.

[figure not shown]
Based on assessments of tolerability, safety, and PK data from all the safety run-in cohorts in Part B, an RD for expansion will be selected. Up to 12 subjects will be enrolled at the RD. If at least 4 subjects show a response by RECIST 1.1 criteria, enrollment will continue up to a total of 30 subjects to evaluate efficacy.

Part C will enroll subjects with previously treated extensive-stage SCLC and consists of safety-run in cohorts followed by an expansion cohort. Part C will follow the same safety run-in schema as described for Part A. See Cohort Table C.

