7.8.1. Replacement of Subjects

A subject enrolled in a safety run-in cohort who withdraws from study before completing the first cycle for reasons other than an AE will be considered to have inadequate data for evaluation by the SRC. In such cases, a replacement subject may be enrolled to receive the same dose of XmAb18087 (and pembrolizumab, when applicable) as the subject who withdrew prematurely. Subjects enrolled in the safety run-in cohorts who are discontinued from the study for any reason after the first cycle will not be replaced.

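### Cohort 4B gives no 4.0 µg/kg dose in Cycle 1, yet the rules for judging it run on Cycle 1 and require no 4.0 exposure with pembrolizumab

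*Protocol*

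**What the plan says.** Protocol Section 7.3 sets 42-day cycles and states that "Part B dose levels are defined in Table 3". In Table 3, Cohort 4B receives XmAb18087 at 0.3, 1.0, 1.0, 2.0 and 2.0 µg/kg on Days 1, 8, 22, 29 and 36 of Cycle 1, with pembrolizumab on Day 15. Cohort 3B has the same Cycle 1. In Cycle 2, Cohort 4B receives 2.0 on Study Day 43 and 4.0 on Study Days 50, 64, 71 and 78, with pembrolizumab on Day 57. The synopsis lists Day 1 of later cycles under 2.0 and again under 4.0, placing the latter on "Days 1, 8, 22, 29, and 36 of all cycles after the first cycle". On either reading, 4.0 begins in Cycle 2.

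The rules that act on the run-in cohorts are these:

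- **SRC timing (7.7).** With no AESC, "the SRC will be convened after all 3 subjects have completed one treatment cycle or discontinued treatment, whichever comes first". With one AESC among the first three, "3 additional subjects will be enrolled in that cohort (up to a total of 6 subjects) prior to convening the SRC".
- **SRC scope (7.7).** "the SRC will decide whether to advance to the next higher dose level cohort based on review of all available safety data".
- **Replacement (7.8.1).** Withdrawal for non-AE reasons before the end of Cycle 1 counts as inadequate data and may be replaced. After that, "Subjects enrolled in the safety run-in cohorts who are discontinued from the study for any reason after the first cycle will not be replaced".
- **Intrasubject escalation (7.4.3).** All subjects in the next higher cohort must have completed the "first cycle of treatment, and the SRC has made the decision that the higher dose level" is tolerable.
- **Continuation (7.4.1).** Dosing past Cycle 1 requires, among other things, clinical benefit as judged by the investigator.
- **Choice of recommended dose (RD) for Part B (synopsis).** "Based on assessments of tolerability, safety, and PK data from all the safety run-in cohorts in Part B".

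None of these sets a minimum number of 4.0 doses, or of subjects treated at 4.0. The SAP adds none.

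**The concern.** A run-in cohort exists to show whether its target dose is tolerable. In every other cohort the Cycle 1 window includes doses at the target, so a Cycle 1 rule is a reasonable minimum. In 4B the window can close before anyone has received the dose under test. A subject who completes Cycle 1 is outside the inadequate-data category even with no 4.0 dose and, on stopping then, is not replaced. Reaching 4.0 also depends on judged benefit, so some attrition at that point is built in.

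The step matters for this drug. Section 11.3.2 says cytokine release syndrome is more likely after the first dose or a first escalated dose. In 4B the step from 2.0 to 4.0 is the seventh XmAb18087 infusion in Table 3. It falls after the required inpatient stays, which are in Cycle 1 only (Section 7.2), and Table 7 schedules no PK or cytokine sample on Cycle 2 Day 8. At stake are the SRC's tolerability decision for 4B, the RD choice it feeds, and escalation of 3B subjects to that level.

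**Working it through.** **Step 1. Target-level doses in Cycle 1 (Tables 2 to 4).**

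| Cohort | Target, µg/kg | Days at target in Cycle 1 | Doses |
|---|---|---|---|
| 1A, 1C | 1.0 | 8, 15, 22, 29, 36 | 5 |
| 2A, 2C | 2.0 | 15, 22, 29, 36 | 4 |
| 3A, 3C | 4.0 | 22, 29, 36 | 3 |
| 1B | 0.3 | 1, 8, 22, 29, 36 | 5 |
| 2B | 1.0 | 8, 22, 29, 36 | 4 |
| 3B | 2.0 | 29, 36 | 2 |
| 4B | 4.0 | none (first on Day 50) | 0 |

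Three 3B subjects who complete Cycle 1 have had 3 × 2 = 6 target doses, and each is followed for 6 days after the second (Day 36 to Day 42). Three 4B subjects who complete Cycle 1 need have had none.

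**Step 2. Exposure at the review.** The documents give neither accrual nor SRC meeting dates, so both are assumed here. Let starts be *g* days apart and let the SRC meet on the third subject's Day 42. The three subjects are then at Days 42 + 2*g*, 42 + *g* and 42. Counting Table 3 doses of 4.0, if all continue:

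- *g* of 3 or less: first subject at Day 48 at most; 0 of 3 exposed.
- *g* = 4 to 7: first subject at Days 50 to 56, second at Day 49 at most; 1 of 3 exposed.
- *g* = 8: Days 58, 50, 42; 2 of 3 exposed, 1 + 1 = 2 doses.
- *g* = 11: Days 64, 53, 42; 2 of 3 exposed, 2 + 1 = 3 doses.
- *g* = 22: Days 86, 64, 42; 2 of 3 exposed, 4 + 2 = 6 doses.

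If the synopsis is read as 4.0 from Day 43, 2 of 3 are exposed at any spacing of a day or more. If the meeting waits until the third subject's Day 50 dose, 3 of 3 are exposed, provided all continue.

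**Step 3. Stopping at the end of Cycle 1.** Assume each subject independently stops then with probability *q* of 20% to 40%. The chance that nobody is exposed is *q*² = 4% to 16% where two could have been, and *q* = 20% to 40% where one could have been.

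**Step 4. What exposure buys.** The chance of seeing at least one AESC among *k* exposed subjects is 1 − (1 − *p*)^*k*. Section 7.8.2 calls 20% acceptable and 40% excessive for the expansion cohorts. Applying those rates to each exposed subject, whatever the follow-up, is an assumption.

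| Exposed *k* | *p* = 20% | *p* = 40% |
|---|---|---|
| 0 | 0% | 0% |
| 1 | 20% | 40% |
| 2 | 36% | 64% |
| 3 | 49% | 78% |

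Two exposed instead of three loses 13 to 14 percentage points. None exposed loses everything.

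**The case against.** The best defence is that Cycle 1 is a floor, not a limit. The SRC reviews all available data, and Section 7.1 adds cumulative data from the whole study, which could include 4.0 monotherapy from 3A and 3C. The AESC definition in Section 7.8 has no end date. The RD rule is not confined to Cycle 1. Escalation needs an SRC decision that the level is tolerable, and approving 4.0 with nobody exposed would strain that wording. Individual dose-hold rules, 4-hour observation and the expansion boundaries remain. Even three exposed subjects would show no AESC 22% of the time at a 40% rate and 51% at 20%, so any cohort of three is weak evidence.

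All of that stands, and it shows that the SRC is free to act well. It does not show that any rule requires 4.0 exposure in combination. Cohorts 3A and 3C give no pembrolizumab, and nothing says they must finish first. The expansion boundaries act only after the RD is chosen, and Tables 5 and 6 set none for the first two subjects.

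Three stronger readings are tempting, and the documents do not support them:

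- **A higher dose could be opened blind.** It could not: 4B is the top Part B cohort.
- **The SRC would never see all three subjects exposed.** That holds only if it meets on the third subject's Day 42; Section 7.7 sets the meeting after that point without a latest date.
- **The 4.0 dose is itself unsafe.** The dose rationale in Section 5.3 is not visible in the public protocol, so this cannot be judged.

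**Conclusion.** The point holds as a gap in the decision rules for one cohort. Cohort 4B is the only run-in cohort with no target-level dose in Cycle 1, and the no-AESC trigger, the replacement rule and the first-cycle condition for escalation are applied to it unchanged. Followed as written, they allow a tolerability decision on 4.0 plus pembrolizumab with few or no exposed subjects. That is certain from Table 3 and Sections 7.4.3, 7.7 and 7.8.1.

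How few is not certain. The range of zero to two of three rests on the SRC meeting on the third subject's Day 42, and the probabilities rest on assumed spacing, stopping and AESC rates.

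A reader might also infer that the trial's findings are affected. They are not: SAP Section 5.1 reports 4 subjects, 2 in Part A and 2 in Part C, so 4B never opened. The rules should be corrected before the design is used again.

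**What to change.** For Cohort 4B only, with no change to any dose:

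1. Hold the SRC tolerability decision until at least 3 subjects have received 4.0 on Days 50 and 64 and been followed to Day 70. This matches what 3B assures: two target doses and 6 days after the second. The fuller alternative is to wait for the end of Cycle 2 (Day 84).
2. Count a subject with an earlier AESC as evaluable, and keep every treated subject in the safety review, because those who reach 4.0 are selected for benefit and recovered toxicity.
3. Allow replacement of subjects who stop for non-AE reasons before that minimum, as an exception to Section 7.8.1 but within the 6-subject maximum.
4. Bar RD selection at the 4B level, and intrasubject escalation to it, before that review.

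The cost is protocol wording and time: 70 − 42 = 28 days (4 weeks), or 84 − 42 = 42 days (6 weeks). It is longer if replacements are needed, since each needs its own follow-up. If 20% to 40% stop at the end of Cycle 1 (assumed), three exposed subjects need 3/0.8 = 3.75 to 3/0.6 = 5 enrolled, so one or two extra. The overall limit already allows six in every run-in cohort (10 × 6 + 22 + 30 + 30 = 142), so it need not change. If six enrolled subjects do not yield three evaluable ones, 4B should not be the RD without an amendment.

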7.8. Criteria for Adverse Events of Specific Concern and Dose Adjustment

The National Cancer Institute's (NCI's) Common Terminology Criteria for Adverse Events (CTCAE), Version 5.0, will be used for grading toxicities, except for CRS, which will be graded using the CRS revised grading system (Section 11.2 or Appendix C; Lee, 2014).

An AESC is defined as an AE or clinically significant abnormal laboratory value (unless clearly attributable to underlying malignancy or concurrent disease) occurring after the initiation of dosing and meeting the criteria listed below:

For Parts A, B, and C:

1. Any Grade 5 toxicity

Version 1.0 Page 51 of 145

- 2. Grade \geq 3 thrombocytopenia lasting \geq 7 days or \geq Grade 3 thrombocytopenia of any duration if associated with \geq Grade 3 bleeding
- 3. Grade 4 neutropenia or Grade 3 febrile neutropenia lasting ≥ 7 days, or Grade 4 febrile neutropenia
- 4. Any \geq Grade 3 nonhematological toxicity, **except**:
 - a. Grade 3 fatigue, asthenia, fever, anorexia, or constipation
 - b. Grade 3 nausea, vomiting, diarrhea, or abdominal pain controlled by medical management that decreases to \leq Grade 2 within \leq 7 days
 - c. Grade 3 alanine aminotransferase (ALT) and/or aspartate aminotransferase (AST) that decrease to \leq Grade 2 within \leq 5 days
 - d. Grade ≥ 3 gamma glutamyl transferase (GGT), unless it occurs with AST, ALT, and/or total bilirubin values that meet AESC criteria
 - e. Grade 3 electrolyte abnormalities that are clinically insignificant, or treatable, and that resolve, with or without intervention, to < Grade 2 in < 72 hours
 - f. Grade 3 or 4 lipase values that are not accompanied by ≥ Grade 3 amylase values or clinical symptoms or radiographic evidence of pancreatitis

Additional Criterion for Part B (combination therapy) only:

1. Any immune related adverse event (IRAE) that requires permanent discontinuation of study drug according to the guidelines in Table 18

Subjects who experience any toxicity should be followed until the toxicity stabilizes or has returned to their baseline level, or until the commencement of a new anticancer treatment.

Refer to Section 10.3 for safety criteria for adjustment or stopping XmAb18087 and pembrolizumab.

7.8.1. Replacement of Subjects

A subject enrolled in a safety run-in cohort who withdraws from study before completing the first cycle for reasons other than an AE will be considered to have inadequate data for evaluation by the SRC. In such cases, a replacement subject may be enrolled to receive the same dose of XmAb18087 (and pembrolizumab, when applicable) as the subject who withdrew prematurely. Subjects enrolled in the safety run-in cohorts who are discontinued from the study for any reason after the first cycle will not be replaced.

